## **6 STUDY PROCEDURES**

Study-specific procedures are detailed below. All assessments will be completed according to the schedule described in [Table S-1](#). Every reasonable effort should be made to complete the required procedures and evaluations at the designated visits and times.

## 6.1 Screening Assessments

### 6.1.1 Mini-Mental State Examination

The MMSE is a brief 30-point questionnaire that is used to quantitatively assess cognition (Folstein et al. 1975). The MMSE includes simple questions and problems in a number of areas: the time and place of testing, repeating lists of words, arithmetic, language use and comprehension, and copying a drawing. The MMSE is being used in this study to screen for cognitive impairment and it will also be used for safety assessment at other time points.

### 6.1.2 Medical History and Demographics

A complete medical history will be obtained from each potential subject, including details of the subject's PD and DPD diagnoses and treatments (including approximate dates of onset).

Subjects may be asked to provide pharmacy or medical records to substantiate the medication history (Section 4.5).

Demographic information, including date of birth, sex, race, and ethnicity will be recorded as well. Any new medical condition reported after the ICF has been signed will be captured as an AE.

### 6.1.3 Massachusetts General Hospital Antidepressant Treatment Response Questionnaire

The MGH ATRQ (Fava and Davidson 1996; Fava 2003) is a clinician-assisted questionnaire that is to be completed only for subjects who are currently taking an antidepressant at Screening. The MGH ATRQ examines a patient's antidepressant treatment history using specific anchor points to define the adequacy of both the dose and duration of each antidepressant course, as well as the degree of symptomatic improvement obtained with each course. This validated questionnaire allows for the determination of inadequate response to antidepressant therapy (Chandler et al. 2010). If taking an approved SSRI/SNRI, subjects should be exposed to an antidepressant for at least 4 weeks at a dose appropriate for this population.

### 6.2.1 Hamilton Depression Scale–17 item

The Hamilton Depression Scale–17 items (HAM-D-17), is a multiple item questionnaire used to provide an indication of depression, and as a guide to evaluate recovery (Hamilton 1960). The questionnaire is designed for adults to rate the severity of depression by probing mood, feelings of guilt, suicide ideation, insomnia, agitation or retardation, anxiety, weight loss, and somatic symptoms. Each item on the questionnaire is scored on a 3 or 5 point scale, depending on the item, and the total score is compared to the corresponding descriptor. A

score of 0-7 is considered to be normal. Scores of 14 or higher indicate moderate, severe, or very severe depression. Assessment time is estimated at 20 minutes.

### **6.2.2 Clinical Global Impression–Severity and Improvement Scales**

The CGI-S scale is a clinician-rated, 7-point scale that is designed to rate the severity of the subject's depression at the time of assessment using the Investigator's judgment and past experience with subjects who have the same disorder (i.e., depression in Parkinson's disease) (Guy 1976).

The CGI-I is a clinician-rated, 7-point scale that is designed to rate the improvement in the subject's depression at the time of assessment, relative to the symptoms at Baseline.

### **6.2.3 Scale of Outcomes in Parkinson's Disease - Sleep Scale**

The SCOPA Sleep Scale was developed for research in Parkinson disease to evaluate nighttime sleep and daytime sleepiness (Marinus et al. 2003). This scale has high internal consistency for the nighttime sleep and daytime sleepiness scales (0.88 and 0.91, respectively), and test-retest reliabilities (0.94 and 0.89, respectively). Scores on the SCOPA Sleep Scale show high correlations between the nighttime sleep scale and the Pittsburgh Sleep Quality Index (0.83), and between the daytime sleepiness scale and the Epworth Sleepiness Scale (0.81). The coefficient of variation of both the nighttime sleep and the daytime sleepiness scale is higher than that of the Pittsburgh Sleep Quality Index and the Epworth Sleepiness Scale, indicating a better ability to detect differences between individuals.

### **6.2.4 EQ-5D-5L**

The EQ-5D-5L is a standardized instrument used as a measure of health outcome (Kind 1996). It measures 5 dimensions (mobility, self-care, usual activities, pain/discomfort, anxiety/depression), each of which has 5 potential responses. The responses record 5 levels of severity (no problems/slight problems/moderate problems/severe problems/very severe problems). Within a particular EQ-5D dimension, the EQ-5D-5L Proxy Version 1 will be used. For this version, a study partner/caregiver (the proxy) is asked to rate the subject's health-related quality of life in terms of (the proxy's) opinion.

## **6.3 Safety Assessments**

### **6.3.1 Physical Examinations**

A general physical examination will be conducted. The physical exam procedures will include the following organ systems:

- Head, ears, eyes, nose, and throat
- Skin

- Cardiovascular
- Respiratory
- Abdomen
- Genitourinary (optional)
- Musculoskeletal
- Lymph nodes

### **6.3.2 Neurological Examination**

A neurological examination (cranial nerves, motor, sensory, reflexes, gait, and coordination) will be conducted.

### **6.3.3 Vital Signs**

Vital signs will include resting respiration rate, sitting systolic and diastolic blood pressure, temperature, and pulse rate. The resting blood pressure should be measured after the subject has been sitting or supine for  $\geq 3$  minutes.

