**Figure S-1 Schematic of Study Design for ACP-103-048**

**Table S-1 Schedule of Assessments for ACP-103-048**

	Screening	Baseline	Week 2	Week 4	Week 6	EOT Week 8 g	Safety Follow-up Week 10
	Visit 1	Visit 2	Visit 3	Visit 4	Visit 5	Visit 6	Visit 7
Study Day(s)	-21 to -1	1	12 to 18	26 to 32	40 to 46	54 to 60	68 to 74
Informed consent	X						
Inclusion/exclusion assessment	X	X					
MGH ATRQ a	X						
Medical history and demographics	X						
Weight, height, BMI	X	X f				X f	
Physical and neurological examination	X					X	
12-lead ECG b	X	X	X			X	
Vital signs c	X	X	X	X	X	X	
Clinical laboratory tests d	X	X				X	
Screen for drugs of abuse	X	X					
Pregnancy test e	X	X				X	
HAMD-17	X	X	X	X	X	X	
C-SSRS	X	X	X	X	X	X	
MMSE	X	X		X		X	
CGI-I			X	X	X	X	
CGI-S		X	X	X	X	X	
SCOPA		X		X		X	
EQ-5D-5L		X		X		X	
UPDRS Part III		X		X		X	
Dispense study drug		X		X			
Study drug accountability			X	X	X	X	
Phone Follow-Up							X
Concomitant medication	X	X	X	X	X	X	X
AE assessment	X	X	X	X	X	X	X

*Abbreviations and notes to this table are on the next page:*

Abbreviations: AE=adverse event; BMI=body mass index; C-SSRS=Columbia-Suicide Severity Rating Scale; CGI-I=Clinical Global Impression–Improvement; CGI-S=Clinical Global Impression–Severity; ECG=electrocardiogram; EOT=end of treatment; EQ-5D-5L=EuroQol-5 dimensions-5 levels; HAMD-17=Hamilton Depression Scale–17 Item; MGH ATRQ=Massachusetts General Hospital Antidepressant Treatment Questionnaire; MMSE=Mini-Mental State Exam; SCOPA-Sleep=Scales for Outcomes in Parkinson’s Disease-Sleep; UPDRS Part III=Unified Parkinson's Disease Rating Scale Part III.

Notes:

- a Applicable only to subjects who are currently taking an antidepressant.
- b 12-lead ECG at Screening is to be completed in triplicate within a 3 minute period. The ECG may be repeated once at Screening in consultation with the Medical Monitor. Single ECG recordings are to be collected at subsequent visits. ECGs can be performed any time before blood sampling or at least 30 minutes after blood sampling during clinic visits
- c Vital signs (sitting or supine [at least 3 minutes] blood pressure, pulse rate, oral temperature, and respiratory rate) will be performed at Screening and each study visit.

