### 1.3.1 Parkinson's Disease Psychosis Program

The scope of the development program for pimavanserin is the largest ever conducted in PDP. At the time of approval, 616 mostly older, late-stage PDP subjects had been evaluated in 16 countries over a span of >10 years. Clinically meaningful efficacy was established in Study ACP-103-020, a 6-week, placebo-controlled Phase 3 study. This efficacy was supported by data from additional short-term Phase 2b/3 studies. In ACP-103-020, pimavanserin 34 mg consistently demonstrated statistically significant efficacy across multiple and independent endpoints, subject subgroups, and sensitivity analyses. Improvements in sleep and daytime wakefulness were also observed. These clinical benefits were achieved without worsening of PD motor symptoms and without a number of other safety concerns associated with atypical antipsychotics.

Pimavanserin is considered to be generally safe and well tolerated. Across all clinical studies of pimavanserin, the most frequently reported treatment-emergent adverse events (TEAEs) were in the central nervous system (CNS), gastrointestinal, and psychiatric systems. Most events were mild to moderate in intensity. The most common CNS TEAEs included dizziness (including postural), headache, and somnolence (drowsiness). Common gastrointestinal disturbances included dyspepsia, nausea, constipation, and vomiting. Severe nausea and vomiting were dose limiting in a few cases. Reported psychiatric conditions included agitation, insomnia, and confusional state. Refer to the current IB for the most up-to-date Reference Safety Information for pimavanserin.

Clinical and nonclinical safety pharmacology studies of pimavanserin suggest that it is a selective 5-HT2A antagonist. The safety profile of pimavanserin has been assessed in a thorough QT study with doses of pimavanserin ranging from 17 to 68 mg. In the Phase 3 PDP program, an average prolongation of approximately 5 to 8 ms was observed with pimavanserin 34 mg.

The US package insert for pimavanserin has a boxed warning that elderly patients with dementia-related psychosis treated with antipsychotic drugs are at an increased risk of death. Pimavanserin is not approved in the treatment of patients with dementia-related psychosis unrelated to the hallucinations and delusions associated with PDP.

Additional information is provided in the pimavanserin IB and in the NUPLAZID® (pimavanserin) US package insert.

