### **6.3.5 Electrocardiograms**

All 12-lead ECGs will be complete, standardized recordings. The subject must rest in a supine position before the ECG is obtained. ECG tracings (paper or electronic) will be reviewed and interpreted by a qualified clinician. ECG tracings and results (ventricular rate, PR, QRS, QT, QTcF, and QTcB intervals) will be included and summarized in the subject's study records. The ECG will be completed in triplicate at Visit 1 (Screening) within 5 minutes, and as a single tracing at all other visits.

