14.3 Vital Signs

Vital signs are assessed at Screening, Baseline, and Weeks 2, 4, 6 and 8/ET visits.

Vital signs including weight, height (only at Screening), and derived BMI will be summarized at Baseline and all post-Baseline visits using descriptive statistics. The change from Baseline values will also be summarized at each post-Baseline visit.

Vital sign values will be considered PCI if they meet both the observed value criteria and the change from baseline criteria listed in [Table 6](#). The number and percentage of subjects with post-Baseline vital signs that are PCI will be summarized at each post-Baseline visit and for overall post-Baseline. For the overall post-Baseline summaries, all post-Baseline values will be considered, including unscheduled and out of window values. Subjects with multiple PCI values for a given parameter will be counted only once for that parameter. For the by-visit summary, the numerator for the percentage is the total number of subjects with a post-Baseline PCI vital sign for the given parameter and visit, and the denominator is the total number of subjects with non-missing values for the given parameter and visit. For the overall post-Baseline summary, the numerator for the percentage is the total number of subjects with at least 1 post-Baseline PCI vital sign for the given parameter, and the denominator is the number of subjects with at least 1 post-Baseline vital sign for the given parameter. A listing of all subjects with any PCI values will be provided.

Table 6 Criteria for Potentially Clinically Important Vital Signs

Vital Sign Parameter	Unit	Criteria ^a		
		Observed Value	And/Or	Change Relative to Baseline
Systolic blood pressure (supine or sitting)	mmHg	≥180	And	Increase of ≥20
		≤90	And	Decrease of ≥20
Diastolic blood pressure (supine or sitting)	mmHg	≥105	And	Increase of ≥15
		≤50	And	Decrease of ≥15
Pulse (supine or sitting)	bpm	≥120	And	Increase of ≥15
		≤50	And	Decrease of ≥15
Weight	kg	Not Applicable		Increase of ≥7%
				Decrease of ≥7%

^a A post-Baseline value is considered a PCI value if it meets both criteria for observed value and change from baseline.

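### Posture for blood pressure and pulse is stated inconsistently and not held constant within a subject, so change from Baseline can include a posture difference that the planned tables cannot separate from drug effect (minor).

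*Protocol*

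**What the plan says.** Protocol 6.3.3 gives two postures in consecutive sentences. The list of vital signs names "sitting systolic and diastolic blood pressure". The next sentence says "The resting blood pressure should be measured after the subject has been sitting or supine" for at least 3 minutes. For pulse, 6.3.3 names no posture.

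Note c to Protocol Table S-1, repeated as note c to SAP Table 1, allows either posture at Screening and each study visit: "sitting or supine [at least 3 minutes] blood pressure, pulse rate, oral temperature, and respiratory rate".

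SAP 14.3 sets the visits: "Vital signs are assessed at Screening, Baseline, and Weeks 2, 4, 6 and 8/ET visits". It summarises change from Baseline at each post-Baseline visit and does not split by posture. In SAP Table 6 the systolic row reads "Systolic blood pressure (supine or sitting"), and the diastolic and pulse rows carry the same label. A blood pressure or pulse value is PCI only if it meets both an observed-value limit and a change limit of 20 mmHg systolic, 15 mmHg diastolic or 15 bpm.

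SAP 5.3 defines Baseline as the last non-missing pre-dose result, with no condition on posture.

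**The concern.** A site can follow the plan exactly and still compare a supine Baseline reading with a sitting later one, or the reverse. Any difference between postures then enters the change from Baseline. The study has one arm (Protocol 9.5), so no control group would show the same shift and cancel it. The planned tables would not reveal it either, because they do not report posture.

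Vital signs are a named safety endpoint (Protocol 2.3.1). The protocol's account of earlier experience adds some context: "The most common CNS TEAEs included dizziness (including postural), headache, and somnolence (drowsiness"). A reader of the safety tables will therefore look at blood pressure falls with some interest. A posture artefact could create an apparent fall or hide a real one.

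**Working it through.** **Step 1: compare the texts.**

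| Place | Posture |
|---|---|
| Protocol 6.3.3, list of vital signs | blood pressure sitting; pulse not stated |
| Protocol 6.3.3, next sentence | blood pressure sitting or supine, at least 3 minutes |
| Protocol Table S-1 and SAP Table 1, note c | sitting or supine, every visit |
| SAP Table 6 | supine or sitting, pooled, for systolic, diastolic and pulse |
| SAP 5.3, Baseline definition | no posture condition |

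The two sentences of 6.3.3 disagree, and the schedule and the SAP follow the wider one. No text supplied fixes one posture, ties later readings to the Baseline posture, or asks for posture to be recorded.

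**Step 2: shift in the mean change.** The documents state no figure to reproduce. They give no posture difference, no blood pressure SD and no switching rate, so every size below is an assumption, including its direction.

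Bias in mean change = d × s, where d is the assumed posture difference and s is the net share switching (share moving one way minus share moving the other).

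| d (mmHg) | s = 0 | s = 0.25 | s = 0.50 | s = 1 |
|---|---|---|---|---|
| 2 | 0 | 0.5 | 1.0 | 2 |
| 5 | 0 | 1.25 | 2.5 | 5 |
| 8 | 0 | 2.0 | 4.0 | 8 |

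For scale, take an assumed SD of change of 12 mmHg. With the 34 evaluable subjects of SAP 3.5, the standard error is 12/√34 = 2.06 mmHg. With the 40 to be enrolled, it is 12/√40 = 1.90 mmHg. A shift at the upper end of the table would be visible against that, and one at the lower end would not.

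**Step 3: PCI counts.** These come from a simulation with no drug effect, one visit, and all 40 subjects switching the same way. Assumptions: systolic mean 130, between-subject SD 15, within-subject SD 8.5; diastolic mean 75, SDs 9 and 6. The systolic change SD is then 8.5 × √2 = 12.0. Expected number of PCI subjects out of 40:

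| Shift (mmHg) | Low systolic (≤90 and fall ≥20) | Low diastolic (≤50 and fall ≥15) |
|---|---|---|
| 0 | 0.09 | 0.09 |
| −2 | 0.14 | 0.18 |
| −5 | 0.28 | 0.48 |
| −8 | 0.52 | 1.12 |

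Upward shifts do less. At +8 mmHg, expected high-systolic PCI goes from 0.02 to 0.14 and high-diastolic from 0.03 to 0.46.

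The systolic change limit alone, without the observed-value limit, would be met by 4.8% of subjects at no shift and 10.6% at −5 mmHg. The two-part rule removes most of that. Pulse was not simulated. Weight PCI does not depend on posture.

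**The case against.** **The sitting reading of 6.3.3.** The list of vital signs specifies sitting blood pressure, and the next sentence can be read as a minimum rest rule only. That reading is fair, but it does not settle the matter: the second sentence, note c and SAP Table 6 all admit supine readings.

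**The ECG schedule.** A reader might infer a systematic shift by visit. ECGs follow a rule that "The subject must rest in a supine position before the ECG is obtained" and are scheduled at Screening, Baseline and Weeks 2 and 8, but not at Weeks 4 and 6. The documents do not support going that far. No text places vital signs during or after the ECG rest, and ECG timing is tied only to blood sampling. On this route Weeks 2 and 8 would match Baseline and only Weeks 4 and 6 would differ. Early-termination visits include an ECG and can fall in the Week 4 or 6 window. The ECG rest is a possible route and no more.

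**Certainty and size.** A reader might also say that the results do mix posture with drug effect, or that an assumed 15 mmHg difference supplies 15/20 = 75% of the systolic PCI change. The first holds only if posture changes within subjects, which nothing shows. The second sizes one half of a two-part rule with a figure not in the documents. Switches in opposite directions also cancel in the mean.

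**What else stands.** The eCRF, dataset specification and programming conventions are not supplied, so posture may already be recorded. A resting reading in one posture would not measure postural change, and dizziness is captured as an adverse event, so the earlier safety experience is context and not proof of harm. Vital signs are summarised descriptively, without a hypothesis test, and a single-arm change from Baseline does not isolate drug effect even with posture fixed.

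**Conclusion.** The contradiction within 6.3.3, and the pooling of postures in the schedule notes and SAP Table 6, are plain from the text. Change from Baseline in blood pressure and pulse can therefore carry a posture difference that the planned tables cannot separate from drug effect.

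The size is unknown. With an assumed difference of 2 to 8 mmHg and a net 50% of subjects switching, the mean shifts by 1 to 4 mmHg. If posture stays constant within subjects, it shifts by nothing. Under the simulation's assumptions, the effect on each blood pressure PCI count is about one subject or fewer per visit even if all 40 switch.

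Severity is minor: this is a descriptive safety summary, and the HAMD-17 analysis is not affected. It is still worth correcting, because the remedy is nearly free and sites cannot resolve the inconsistency themselves.

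**What to change.** - **Wording.** Reconcile the posture text in Protocol 6.3.3, note c of Protocol Table S-1 and SAP Table 1, and SAP Table 6, and say explicitly what applies to pulse.
- **Conduct.** Require each subject's later readings in the posture used at Baseline, and record posture on the eCRF if it is not already captured.
- **Analysis (SAP 14.3).** Keep every post-Baseline value in the PCI counts and listings, and flag those whose posture differs from Baseline or is unknown. Add a sensitivity summary of change from Baseline restricted to same-posture pairs. Do not restrict the PCI counts to those pairs. SAP 5.3.2 and 14.3 count all post-Baseline values for the overall PCI summary, and dropping some because of posture could hide an extreme value.

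**Cost.** One site instruction, possibly one eCRF field, and one extra descriptive table. No new visit or procedure is needed. The limitation is that posture may not be recoverable for readings already taken: 9 subjects had completed Week 8 when the sample size was reviewed (SAP 3.5). Those readings would be flagged as unknown posture and left out of the sensitivity summary only.

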### **6.3.4 Height, Weight, and Body Mass Index**

Height will be measured in centimeters.

Weight will be measured in kilograms.

Body mass index (BMI) will be calculated using the following formula:

$$\text{Weight (kg)} / [\text{height (m)}]^2$$

### **6.3.5 Electrocardiograms**

All 12-lead ECGs will be complete, standardized recordings. The subject must rest in a supine position before the ECG is obtained. ECG tracings (paper or electronic) will be reviewed and interpreted by a qualified clinician. ECG tracings and results (ventricular rate, PR, QRS, QT, QTcF, and QTcB intervals) will be included and summarized in the subject's study records. The ECG will be completed in triplicate at Visit 1 (Screening) within 5 minutes, and as a single tracing at all other visits.

### **6.3.6 Columbia-Suicide Severity Rating Scale**

The C-SSRS monitors changes in suicidal thinking and behavior over time, in order to determine risk (Posner et al. 2011). The following 4 constructs are measured: the severity of ideation, the intensity of ideation, behavior, and lethality.

The C-SSRS will be used to assess suicidal ideations and behaviors. The Baseline/Screening version will be administered at Visit 1 (Screening), and the Since Last Visit version will be

administered at subsequent visits. The C-SSRS results for each subject should be reviewed by the Investigator at each visit. If at any time the C-SSRS results for a given subject reveal potential suicidality, then the Investigator should assess the clinical significance of such results. If a clinically significant risk of suicidality is identified for a subject, then the Investigator should discontinue the subject and implement appropriate treatment (Section 4.4).

### 6.3.7 Unified Parkinson's Disease Rating Scale

The UPDRS is a comprehensive battery of motor and behavioral indices derived from the Columbia Scale (Goetz et al. 2007), providing explicit rating criteria that have undergone testing for reliability. Only Part III (motor examination) will be administered.

The UPDRS assessments should be conducted in the "on" state. This will ensure that noise associated with a subject's "on/off" status does not confound interpretation of the motor function data.

### 6.3.8 Laboratory Evaluations

The laboratory evaluations will include, but are not be limited to, the following:

Clinical chemistry tests

- Sodium (Na), potassium (K), chloride (Cl), phosphorus (P), calcium (Ca), carbon dioxide (CO2), blood urea nitrogen (BUN), creatinine (CR), uric acid
- Alanine aminotransferase (ALT), aspartate aminotransferase (AST), gamma-glutamyl transpeptidase (GGT), alkaline phosphatase (ALP), total bilirubin (TBIL), lactate dehydrogenase (LDH)
- HbA1c
  - HbA1c test should only be performed at Visit 1 (Screening), and Visit 6/EOT
- Glucose
- Prolactin
- Thyroid stimulating hormone (TSH) and free T4
  - TSH and free T4 reflex will only be performed at Visit 1 (Screening). A free T4 reflex will only be done if the TSH is outside of the reference lab normal range.
- Lipid Panel

